6.4. Derived and Transformed Data

6.4.1. Sustained Conversion

For subjects who convert (ie, 3-consecutive negative monthly MAC cultures), the conversion will be considered ‘sustained’ if there are no positive solid media and no more than 2 consecutive positive monthly broth MAC cultures from conversion through End of Treatment.

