### 7.2.2 Sputum Collection, Transport, and Assessment

Pre-dose expectorated or induced sputum specimens (approximately 3 mL) are required at every scheduled visit during the treatment phase. To improve the probability of obtaining a good sputum specimen, it is recommended that at least 2 sputum samples will be obtained from each subject for each study visit at which sputum is collected. One sputum sample will be collected on one of the 2 days prior to a scheduled visit. Subjects will refrain from administering LAI on the days' sputum is obtained, starting 2 days prior to the scheduled visit, even if a spontaneous sputum cannot be obtained by the subject at home. If a subject is unable to produce sputum spontaneously, one induced sputum specimen at the site will be acceptable. At the scheduled visit, once sputum is collected (spontaneously or by induction), the administration of LAI can recommence. Sites are encouraged to notify subjects by telephone of this procedure 3 days prior to their scheduled visit. If a subject is unable to produce sputum independently, sputum may be induced as described in [APPENDIX 1](#) at the clinical site only, if these suggestions are safe for the subject. If a subject is still unable to produce sputum despite reasonable efforts, this will be recorded as a negative culture result at that time point.

Protocol Amendment 3.1: 25 May 2017

*This protocol is solely for communicating information about the investigational drug between Inmed Incorporated and study personnel. Information is not to be reproduced, abstracted or used for sharing of information for any other purpose, whatsoever, except with the written permission of Inmed Incorporated.*

Confidential

Sterile, leak proof, non-wax, disposable plastic containers labeled with 2 subject identifiers will be used to collect specimens aseptically to avoid contamination. Sputum samples should be refrigerated, not frozen, until shipped to the central microbiology lab within 2 days of collection to avoid overgrowth by contaminating normal flora. No fixative or preservatives are to be used with sputum samples. Detailed instructions for collecting, processing, and shipping sputum specimens will be provided in the site laboratory manual.

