3.2.2. Secondary Endpoints

The secondary efficacy endpoints are:

1. Proportion of subjects achieving culture conversion (3 consecutive monthly negative sputum cultures without relapse or recurrence) by Month 12/EOT.
2. Proportion of subjects achieving culture conversion by Month 6.
3. Time to culture conversion. The date of conversion is defined by the date of the first of at least 3 consecutive monthly culture specimens that are MAC negative.
4. The mean change from Baseline in 6MWT distance a Month 6 and Month 12/EOT

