6.4.9. Visit Windows

Nominal visit windows will be used for all visits, except for EOT and EOS visits. Because EOT and EOS visits are conducted in place of the planned visit for subjects who prematurely end treatment or study participation, these visits also need to be mapped to the coincident visit.

For example, a subject discontinues treatment at the Month 4 visit. The site will conduct the EOT visit at Month 4 rather than the Month 4 visit, but for analysis purposes this visit should be used for the Month 4 summary as well as the EOT summary. Similarly, for the EOS visit. Thus, should it be appropriate, the EOT and EOS visit need to be mapped to the corresponding visit. Should the EOT or EOS visit map to a time that doesn't coincide with a scheduled visit, it will not be mapped.

Subjects who prematurely discontinue from the study, may not have an EOT visit. In this case the EOS visit will also be the EOT visit and should be mapped accordingly.

Table 4: Visit Windows (Days)

Visit Name	Visit Number	Target Anchor	Relative Target Day	Visit Window
Baseline	1	Last visit from Study INS-212	1	-2 to 1
Month 1	2		30	23 to 37
Month 2	3		60	53 to 67
Month 3	4		90	83 to 97
Month 4	5		120	113 to 127
Month 5	6		150	143 to 157

Visit Name	Visit Number	Target Anchor	Relative Target Day	Visit Window
Month 6	7		180	173 to 187
Month 7	8		210	203 to 217
Month 8	9		240	233 to 247
Month 9	10		270	263 to 277
Month 10	11		300	293 to 307
Month 11	12		330	323 to 337
Month 12 (EOT)	13		365	353 to 367
Month 13 (EOS)	14		420	413 to 427

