6.4.10. Multiple Assessments

Sputum samples will be captured daily starting two days before each visit. Thus, each visit will have up to three sputum samples. For the determination of culture conversion, should any sputum samples at that visit be MAC culture positive, that visit is considered positive for MAC. When determining if a subject had 3-consecutive monthly negative sputum cultures, only schedule monthly samples will be used. However, subjects with a positive unscheduled sputum sample culture among the 3-consecutive monthly negative sputum cultures will not be deemed as achieving culture conversion.

For the determination of sustained culture conversion, if a subject has any positive solid media culture whether scheduled or unscheduled after conversion or with at least 3 consecutive positive scheduled monthly liquid media cultures, that subject will not have achieved sustained culture conversion.

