6.5. Handling of Missing Data

6.5.1. Missing Efficacy Endpoints

6.5.1.1. Conversion

A sputum culture will be considered missing at the visit only if there are no sputum samples at that visit to culture. Visits with missing sputum cultures prior to subject converting will be considered as positive cultures. This results in the most conservative outcome, ie, most conversion failures.

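### Final SAP 6.4.1 counts a converter who withdraws or misses later visits as sustained unless a relapse was observed, so the sustained-conversion rate is an upper bound

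*SAP*

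**What the plan says.** **Rule for sustained conversion.** Final SAP 6.4.1 asks for no solid-media positive and "no more than 2 consecutive positive monthly broth MAC cultures from conversion through End of Treatment". Section 6.4.10 puts the same rule the other way round: sustained status is lost "if a subject has any positive solid media culture whether scheduled or unscheduled after conversion", or when at least three scheduled monthly liquid cultures in a row are positive. Neither section asks for a minimum number of cultures after conversion.

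**Rule for missing cultures.** Final SAP 6.5.1.1 says "Visits with missing sputum cultures prior to subject converting will be considered as positive cultures" and gives the reason: "This results in the most conservative outcome, ie, most conversion failures". It defines missing narrowly: "A sputum culture will be considered missing at the visit only if there are no sputum samples at that visit to culture". No rule covers missing cultures after conversion. The SAP for the accelerated submission (10.1, 10.4) deals with missing cultures when deciding who converted, but does not mention sustained conversion.

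**Where End of Treatment falls.** Final SAP 6.4.9 maps early visits "Because EOT and EOS visits are conducted in place of the planned visit for subjects who prematurely end treatment or study participation". The schedules of events (protocol Table 3-1, final SAP 11.3) show no sputum collection at End of Study.

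**Subjects with no sputum.** Protocol 7.2.2 says that if a subject is still "unable to produce sputum despite reasonable efforts, this will be recorded as a negative culture result at that time point".

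**Where it is reported.** Secondary endpoint 1 (final SAP 3.2.2) is "Proportion of subjects achieving culture conversion (3 consecutive monthly negative sputum cultures without relapse or recurrence) by Month 12/EOT". Sustained conversion has its own table, 14.2.2, arranged by time since conversion.

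**The concern.** Before conversion the plan treats absence of evidence as failure and calls this conservative. After conversion the same absence counts in the subject's favour, because only an observed positive can remove sustained status. The date of conversion is that of the first of the three negatives (3.2.2), so those three cultures alone can satisfy the rule when treatment ends at the third.

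A durability measure is meant to show whether a conversion lasts. Under this rule the people about whom least is known are scored as lasting successes, and the reported proportion stays high however many of them there are. Results are also described by INS-212 arm, so unequal loss of follow-up between the arms would distort that description as well.

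**Working it through.** The documents give no figure for sustained conversion, so there is nothing of the plan's own to reproduce. The check has two parts.

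**1. Applying the rules as written.** Each string shows Months 1 to 12: N negative, B broth-positive only, S solid-positive, M missing. The third column follows final SAP 6.4.1, 6.4.10 and 6.5.1.1. The last column scores any missing culture after conversion as failure, for contrast only.

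| Months 1–12 | Situation | As written | Missing after conversion = failure |
|---|---|---|---|
| NNNNNNNNNNNN | converts, negative throughout | sustained | sustained |
| NNNMMMMMMMMM | converts, then leaves | sustained | not sustained |
| NNNBBMMMMMMM | converts, two broth positives, then leaves | sustained | not sustained |
| NNNBBMBNNNNN | a missed month breaks a run of broth positives | sustained | not sustained |
| NNNNNNNSNNNN | solid positive at Month 8 | not sustained | not sustained |
| NMNNSSSSSSSS | Month 2 missing before conversion | not a converter | not a converter |
| SSSSSSSSSNNN | converts at Months 10–12 | sustained | sustained |

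The second and sixth rows show the asymmetry: one missing month before conversion costs the subject conversion status, while nine missing months after it cost nothing. The last row is a completer for whom no later scheduled culture exists. That is the end of planned sampling, not loss to follow-up.

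**2. Size, with assumed inputs.** Take 50 converters, 5 observed relapses, and k leavers with no positive seen (k = 5, 10, 15). None of these numbers comes from the documents.

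- Plan as written: (50 − 5)/50 = 90% for every k.
- All leavers counted as failures: (50 − 5 − k)/50 = 80%, 70%, 60%.
- Leavers assumed to relapse at the same rate as those followed: 1 − 5/(50 − k) = 1 − 5/45, 1 − 5/40, 1 − 5/35 = 88.9%, 87.5%, 85.7%.

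The plan is therefore 10, 20 or 30 points above the worst case, but only 1.1, 2.5 or 4.3 points above the same-rate case.

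**In general.** Let d be the share of converters lost before any relapse is seen and r the relapse rate among those followed.

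- As written: 1 − (1 − d)r.
- Leavers as failures: (1 − d)(1 − r).
- Difference: exactly d, whatever the number of converters.
- Excess over the same-rate value 1 − r: d × r.

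For d from 10% to 30% and r from 10% to 20%, the plan's rate is 82% to 93% and the leavers-as-failures rate is 56% to 81%. The excess d × r runs from 0.1 × 0.1 = 1 point to 0.3 × 0.2 = 6 points.

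**The case against.** The strongest reply has five parts.

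- **The rule mirrors the protocol.** Protocol 7.2.3 defines relapse or recurrence by observed positives, and the endpoint runs to Month 12/EOT, which for an early stopper is the early visit. This is true, but it explains the rule rather than curing it: for someone who leaves at Month 3 the phrase covers no durability period at all.
- **Zero follow-up is an extreme case.** Protocol 4.3 and 5.11 call for an EOT visit on early discontinuation, and 6.3 recommends sputum there. Many leavers would have one culture after their last monthly visit. However, SAP 6.4.9 accepts that some will have no EOT visit and lets the EOS visit stand in, and no sputum is scheduled at EOS. Even one extra culture is little follow-up.
- **Non-producers are covered by the protocol.** Under 7.2.2, inability to produce sputum despite reasonable efforts is recorded as negative. This stands. A reader might infer that SAP silence makes every subject without sputum sustained; for this group the result comes from an explicit rule. What remains is that 6.5.1.1 treats a visit without a sample as missing, hence positive before conversion, and the two sections are not reconciled.
- **Table 14.2.2 may already show who was followed.** Final SAP 11.2 places the mock-ups in separate documents, so this cannot be ruled out. The SAP text gives no denominator or follow-up requirement.
- **Little depends on it.** The primary endpoint is safety, efficacy is descriptive and no hypothesis is tested. That limits the weight of the point, not its correctness.

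**Conclusion.** The point holds and should be settled before database lock, as a secondary descriptive matter. As written, the plan counts converters who withdraw or miss later visits as sustained unless a qualifying relapse was observed, so the sustained rate is an upper bound. Its distance from the worst case equals the share of converters lost: 10 to 30 points for the assumed losses of 10% to 30%. The true value lies between the two.

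Four stronger readings are not supported:

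- The 10 to 30 points are not the bias. They assume that every leaver relapsed; with equal relapse rates the excess in the example is 1.1 to 4.3 points.
- The SAP does not say in words that dropouts are sustained. This follows from the rule together with the absence of a missing-data rule after conversion.
- It is not shown that secondary endpoint 1 itself is computed this way. Its wording includes durability, but final SAP 8.6.1 does not mention sustained status, and Table 14.2.1 reports conversion separately. The link is an inference.
- The rule does not require every later culture to be negative. Up to two consecutive broth positives are tolerated.

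**What to change.** 1. Add to final SAP 6.5.1.1: after conversion, a subject with no further cultures because of withdrawal or missed visits before the planned Month 12 visit is counted as not sustained at time points after the last observed culture.
2. State that a subject who completes Month 12 sampling is not assessable, rather than failed, at times from conversion that fall beyond Month 12. For example, a completer whose first negative is at Month 8 can be followed for 12 − 8 = 4 months and should leave the denominator after that.
3. In Table 14.2.2, show the number of converters with an observed culture at each time point, and keep the current observed-positive version as supportive.
4. Reconcile protocol 7.2.2 (no sputum despite reasonable efforts is recorded negative) with SAP 6.5.1.1 (no sample is missing, and positive before conversion), and state which applies after conversion. Non-production must be kept apart from a missed visit or withdrawal, or item 1 could override the protocol.

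The cost is a few sentences in the SAP and one supportive version of a table; no new data are needed. The sustained rate will look less favourable. Counting all leavers as failures is itself a lower bound, which is why both versions should be shown.

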6.4.2. Baseline Age

Use subject’s age as reported on the CRF.

6.4.3. Study Day

Study day, the number of days from enrollment, is derived using the following formula:

$$\text{STUDYDAY} = (\text{assessment} - \text{enrollment date}) + (\text{assessment} \geq \text{enrollment date});$$

there is no study day 0.

6.4.4. Study Month

Study month, the number of months from enrollment is derived using the following formula:

$$\text{STUDYMON} = \text{STUDYDAY}/30.$$

6.4.5. Duration

Duration is the time between two dates and may be expressed in days, months, or years. The formulae for deriving duration are:

- Duration (days) = end – start dates + 1
- Duration (months) = (duration [days])/30.4
- Duration (years) = (duration [days])/365.25

6.4.5.1. Total Duration

Total duration is the duration within a reporting group (eg, SOC). Total duration is derived with the subject and is the sum of all durations in the reporting group.

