### 8.2.3 Assessment of Outcome

The Investigator will record the outcome of the AE as either resolved or ongoing on the AE page of the eCRF. AEs of unknown outcome will be considered as ongoing for purposes of AE reporting.

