6.4.5.3. Mean Duration

Mean duration is the average duration within a reporting group (eg, SOC), derived as the total duration divided by the number of events in the reporting group.

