6.5.3. Missing Start and Stop Dates for Adverse Events

For AEs, missing or incomplete onset or end dates will be imputed such that the AE is assumed to have occurred during the study treatment phase (i.e., considered a TEAE) unless the partial onset date or end date, indicates differently. If time is needed for analysis purpose, all missing or partial times will be replaced by 00:00 (HH:MM) for start times and 23:59 for stop times using 24-hour clock.

The following algorithm will be applied to missing and incomplete onset and end dates, end dates should be imputed before onset dates:

Adverse Event End Dates

- If the end date is completely missing or the year portion of end date is missing (even if day or month are present), or the AE is ongoing, then set the end date to the last available subject visit date.

- If the month portion of the end date is missing and the year is present, then set the month to December.
- If only the day portion of the end date is missing, then set the day to the last day of the month.

Adverse Event Onset Dates:

- If the imputed end date is on or after the first dose of study drug (ALIS), then impute the missing portion of the onset date as follows:
 - If only the day portion of the onset date is missing, and the month and year are the same as the month and year of the first dose of ALIS; otherwise the missing day will be set to the first ('01') of the month.
 - If month portion of the onset date is missing and the year is present, and the year is the same year as the first dose of ALIS; otherwise set the month to January ('JAN').
 - If the onset date is completely missing or the year portion of onset date is missing, the onset date will be imputed to the date of first dose of ALIS.
- If the imputed end date is before the first dose of study drug (ALIS), then impute the missing portion of the onset date as follows:
 - If only the day portion of the end date is missing, then set the day to the first ('01').
 - If the month portion of the onset date is missing and the year is present, then set the month to January ('JAN').
 - If the onset date is completely missing or the year portion of onset date is missing, then set the year to the end date year.
- After onset dates have been imputed, check that the imputed onset date is on or before the imputed end date. If imputed onset date is after the imputed end date, set the imputed onset date to the imputed end date.

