9.2.2. Summaries of Duration of Adverse Events

The duration of serious AEs, serious AEs resulting in hospitalization, and AEs in the ‘respiratory, thoracic and mediastinal disorders’ body system will be summarized.

The duration of AEs will be summarized (n, mean, standard deviation, median, minimum, and maximum) for each system/organ class and preferred term within the system organ class. The total duration is the sum of the duration for all AEs within a subject at the SOC level, for the SOC summaries and within the preferred term for preferred term summary. The maximum duration is the maximum of the durations for all AEs within a subject at the SOC level, for the SOC summaries, and within preferred term for the preferred term summary. The mean duration is the mean of the durations for all AEs within a subject at the SOC level, for the SOC summaries, and within preferred term for the preferred term summary.

The summary table of AE durations will also include a tabulation of the number of events per subject reported in the summary level (ie, SOC, preferred term level).

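### Ongoing adverse events are closed at the last visit and summarised as completed durations, so the descriptive duration tables understate unresolved events

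*SAP*

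**What the plan says.** Final SAP 6.4.5 computes every duration as "Duration (days) = end – start dates + 1". For an adverse event with no end date the end has to come from somewhere, and 6.5.3 supplies it. If the date is wholly missing or lacks the year, "or the AE is ongoing, then set the end date to the last available subject visit date". Protocol 8.2.3 widens the group concerned: "AEs of unknown outcome will be considered as ongoing" for reporting purposes.

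Final SAP 9.2.2 applies durations to three sets of events: "The duration of serious AEs, serious AEs resulting in hospitalization, and AEs in the" respiratory, thoracic and mediastinal system organ class (SOC). It specifies that "The duration of AEs will be summarized (n, mean, standard deviation, median, minimum, and maximum" are shown by SOC and preferred term, with a tabulation of the number of events per subject. It gives no censoring rule and no separate display of resolved and ongoing events.

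On totals, 6.4.5.1 says the figure "is the sum of all durations in the reporting group". Section 9.2.2 repeats this: "The total duration is the sum of the duration for all AEs within a subject at the SOC level". Mean duration (6.4.5.3) is "derived as the total duration divided by the number of events in the reporting group".

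**The concern.** The time from onset to last visit for an unresolved event is a lower bound on its duration. Putting it into a mean, median or maximum beside true durations treats the bound as the answer. The events most affected are those that persist to the end of follow-up, including events in subjects who stop early, whose end-of-study visit comes about a month after end of treatment (Protocol 6.4). A reader using these tables to judge how long respiratory complaints last on an inhaled drug would see them as shorter than they were, and nothing specified for the tables would show how many were still open.

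The total-duration statistic raises a smaller question of reading. One respiratory episode can be coded to several preferred terms, and at SOC level their days are added even when they coincide.

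**Working it through.** There is no figure in the plan to reproduce. All event dates and duration distributions below are assumptions, because the documents give none.

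**1. Single ongoing events, by the formula in 6.4.5.**
- Onset day 381, last visit day 395, assumed true end day 440. The table uses 395 − 381 + 1 = 15 days; the truth is 440 − 381 + 1 = 60 days.
- Early stop: onset day 100, last visit day 120, assumed true end day 300. The table uses 120 − 100 + 1 = 21 days; the truth is 300 − 100 + 1 = 201 days.

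The shortfall is always true end minus last visit (45 and 180 days here), so for an event still open after the last visit the direction is fixed by the rule.

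**2. Effect on a summary row.** Assume exponential true durations, and follow-up remaining after onset uniform over 1 to 395 days (395 = 365 + 30) and independent of duration; 400,000 simulated events per scenario.

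| True mean | Ongoing at last visit | Mean, closed at last visit | True median | Median, closed at last visit | Mean, resolved events only |
|---|---|---|---|---|---|
| 30 | 7.4% | 27.7 | 20.8 | 19.3 | 27.5 |
| 60 | 15.0% | 51.0 | 41.6 | 36.0 | 49.4 |
| 120 | 29.1% | 85.1 | 83.2 | 62.7 | 76.7 |

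The means can be checked by hand. For exponential durations, the expected closed duration is the true mean times the share resolved: 30 × 0.926 = 27.8, 60 × 0.850 = 51.0, 120 × 0.709 = 85.1. The first differs from the table by simulation error only. The true medians are the mean × ln 2. The median falls short by 1.5, 5.6 and 20.5 days. A Kaplan-Meier estimate on the same data, with ongoing events censored, recovers the true medians.

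The last column matters for the choice of remedy. Dropping unresolved events gives means slightly further from the truth than closing them at the last visit.

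**3. Total duration with overlapping events, one subject, one SOC.**
- Days 10–39 and 40–69 (no overlap): 30 + 30 = 60, against 60 distinct days.
- Days 10–39 and 25–54: 30 + 30 = 60, against 45 distinct days (days 10–54).
- Days 10–300 and 20–300: 291 + 281 = 572, against 291 distinct days and a study of at most 13 months.

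The excess is exactly the overlapping days (0, 15 and 281). Overlap does not inflate the maximum (30, 30, 291) or the per-event mean (30, 30, 286).

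**4. Dependency between definitions.** If total duration were redefined as distinct days and 6.4.5.3 left alone, two concurrent 60-day events would give a mean of 60 / 2 = 30 days, although each lasted 60.

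**The case against.** Several points on the other side stand.

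- **Purpose of 6.5.3.** It is framed around deciding whether an event is treatment-emergent, and it does not say that 9.2.2 uses the imputed dates. Table mock-ups are in separate documents, so a footnote or a count of ongoing events there cannot be excluded. However, 6.5.3 sets the end date without restriction, and 6.4.5 offers no other end for an ongoing event.
- **Serious events.** Protocol 8.5 requires serious events, including those open at end of study, to be followed to resolution or stabilisation or until otherwise explained. Many will have real end dates. Protocol 5.11 has a similar rule for events leading to treatment withdrawal. This narrows the exposure mainly to non-serious respiratory events. It does not remove it: outcome is recorded only as resolved or ongoing, so an event that has merely stabilised remains ongoing.
- **Partial end dates are imputed late**, to the last day of the month or to December. Those durations are lengthened. A reader might infer that the duration tables as a whole are biased downward; the documents do not support that.
- **Total duration is openly defined as a sum** and is shown with the number of events per subject. A reader might infer that the tables wrongly double-count days. As event-days the sum is coherent, only that one statistic is affected, and what is missing is a label.
- **Importance.** Duration tables are descriptive and supplementary. Incidence, severity, relatedness, withdrawal and interruption tables do not use duration.

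**Conclusion.** The point holds as a minor flaw in descriptive tables. Followed as written, 6.5.3 and 9.2.2 together report unresolved and unknown-outcome events as completed durations that are too short. The direction for those events follows from the rule. The size does not: the shortfalls of 1.5 to 20.5 days in the median rest on assumed exponential durations, independent uniform follow-up and assumed true means of 30 to 120 days.

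The tables concerned are 14.3.1.10, 14.3.2.10, 14.3.2.11.3, 14.3.6.10 and 14.3.7.10, with the hospitalisation-duration tables 14.3.3.3.3, 14.3.4.3.3 and 14.3.5.3. It would go too far to infer that the primary safety endpoint is affected. That endpoint is a set of frequencies (final SAP 3.2.1), which do not depend on how long an event is said to last.

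**What to change.** In final SAP 9.2.2:

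- Treat events ongoing or of unknown outcome as censored at last contact, and define last contact.
- Report a Kaplan-Meier median event duration for each SOC and preferred-term row, printed as not reached where it cannot be estimated, and show the number of events ongoing in that row.
- State that events cluster within subject, so any confidence interval must allow for it. State also that censoring may be informative where a persistent event led to withdrawal.
- Do not use resolved-only durations as the main summary.

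The imputed dates in 6.5.3 can stay for treatment-emergent classification.

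In 6.4.5.1, label total duration as event-days, or add a separate count of distinct calendar days with at least one event. Keep mean duration as the sum of event durations divided by the number of events, so that 6.4.5.3 still works.

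The cost is modest reprogramming of descriptive tables. Event dates and outcomes are already on the eCRF, and final SAP 8.6.2 already specifies Kaplan-Meier code with censoring for culture conversion. No new data are needed.
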